6. Applied 20% topical benzocaine jelly (Ultradent Products Inc, South Jordan, UT) after thoroughly drying the tissues surrounding the inferior alveolar nerve block (IANB) injection site, buccal vestibule, and lingual vestibule of the treatment tooth (about 1 minute)
7. The student researcher administered the 2 IANBs (about 2 minutes) and then started the timer immediately
8. The patient was regularly re-assessed for soft tissue anesthesia (as previously described)
 - a. If within 10 minutes the patient had confirmed soft tissue anesthesia, then the IANBs were considered successful, and 1 cartridge of the respective

anesthetic formulation was supplementarily administered via apical buccal and lingual infiltrations (documented exact time elapsed)

- b. If at 10 minutes the patient did not have any indications of soft tissue anesthesia, then IANBs would be considered missed, and the patient would be withdrawn from the study. Administer additional local anesthetic as clinically appropriate

9. Tested the treatment tooth using EPT in 2-minute intervals (starting at 2 minutes post-supplementary infiltrations)
 - a. If within 20 minutes post-IANBs pulpal anesthesia was confirmed with 2 consecutive EPT=80, initiated NSRCT (document exact time elapsed)
 - b. If at 20 minutes post-IANBs pulpal anesthesia was not confirmed with 2 consecutive EPT=80, anesthesia was considered a failure, and additional local anesthetic was administered as clinically appropriate
10. All pertinent data, including the patient's VAS comfort assessment after pulp chamber access/pulpotomy, were recorded and analyzed with the help a professional statistician for statistical significance.

STATISTICAL ANALYSIS

The buffered anesthetic and unbuffered anesthetic groups were compared for differences in the percentage of subjects who achieved profound pulpal anesthesia using chi-square tests. The time needed to achieve profound pulpal anesthesia using buffered anesthetics and unbuffered anesthetics was compared using Kaplan-Meier survival curves and log-rank tests. A 5% significance level was used for all tests. Comparisons of the VAS results were made using a

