Wilcoxon Rank Sum test. Up to 60 subjects were randomized to ensure that 40 evaluable subjects could complete the study. With a sample size of 20 subjects per group, the study had an 80% power to detect a difference between 90% and 50% of subjects who achieved profound pulpal anesthesia. Calculations were based on a chi-square test with a two-sided 5% significance level. Sample size calculations were performed using PASS 2019 (NCSS, LLC. Kaysville, UT). All calculations were derived with professional assistance.

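### Three between-group tests are each run at 5% with no named primary endpoint or testing order; if any one may carry a claim, the chance of a false claim of a difference is about 8-13%

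*Combined protocol and SAP*

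**What the plan says.** The Statistical Analysis section lists three comparisons between the buffered and unbuffered groups:

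- The first is on "differences in the percentage of subjects who achieved profound pulpal anesthesia using chi-square tests".
- The second is on onset: "The time needed to achieve profound pulpal anesthesia using buffered anesthetics and unbuffered anesthetics was compared using Kaplan-Meier survival curves and log-rank tests".
- The third is on the VAS results, by a "Wilcoxon Rank Sum test".

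On the error rate it says only: "A 5% significance level was used for all tests". No endpoint is called primary or secondary. There is no order of testing, no division of the 5% and no rule for which result decides the trial.

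The one sign of priority is in the sample size paragraph: "With a sample size of 20 subjects per group, the study had an 80% power to detect a difference between 90% and 50" percent. It adds: "Calculations were based on a chi-square test with a two-sided 5% significance level".

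Two other places bear on the point. Anesthetic Testing and Documentation ties profound pulpal anesthesia to an EPT reading of 80, but later classes a VAS score of 3 or lower as success in obtaining profoundness. Step 10 of Study Procedures says that all pertinent data were analysed for statistical significance, without ranking them.

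**The concern.** Under the stated rule, each of three results can reach significance on its own, and the plan does not say which one the conclusion rests on. The 5% used for the sample size is the error rate of the chi-square test alone. It is not the error rate of a conclusion that may draw on whichever test turns out significant.

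This has practical weight in a trial of this size. With 20 per group the trial is powered for a very large difference, 90% against 50%. A non-significant chi-square beside a significant onset or VAS result is a realistic outcome, and the plan gives no guidance on how to report it.

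**Working it through.** **Inputs from the documents.** 20 evaluable per group; 90% vs 50%; two-sided 5% for each test; EPT read every 2 minutes; failure if two consecutive readings of 80 are not obtained within 20 minutes of the blocks.

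**Inputs assumed, because the documents give none.** The EPT success rate common to both arms under no difference (50%, 70%, 90%); the latent correlation between VAS and onset time (0 to 0.9); and 70% of participants with VAS of 3 or lower.

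**Step 1: the plan's own figure.** Normal approximation with pooled variance under the null and no continuity correction, mean proportion (0.9 + 0.5)/2 = 0.7:

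z = [0.4 × √20 − 1.960 × √(2 × 0.7 × 0.3)] / √(0.9 × 0.1 + 0.5 × 0.5) = (1.789 − 1.270) / 0.583 = 0.889

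Power = Φ(0.889) = 0.813, so the stated 80% with 20 per group is reproduced. Exact power of the uncorrected test is 83.8%. With a continuity correction, power would be 72.6% and 25 per group would be needed, so the stated figure points to the uncorrected test.

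**Step 2: reference values for several tests at 5%.**

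- Three independent tests: 1 − 0.95³ = 14.3%.
- Two independent tests: 1 − 0.95² = 9.75%.
- Upper bound for three tests: 3 × 5% = 15%.

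**Step 3: allowing for dependence.** Trials with no true difference were simulated, 20 per group and 20,000 per scenario. Onset was recorded on 2-minute readings, failures were censored at 20 minutes, VAS was a skewed 0-10 score, and the chi-square was uncorrected. The chance that at least one of the three tests is significant was:

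| Chi-square success definition | EPT success rate | Corr. 0 | 0.3 | 0.6 | 0.9 |
|---|---|---|---|---|---|
| EPT only | 50% | 10.4% | 10.5% | 9.9% | 8.7% |
| EPT only | 70% | 11.9% | 11.7% | 10.7% | 9.7% |
| EPT only | 90% | 12.0% | 12.1% | 11.3% | 10.0% |
| EPT and VAS ≤ 3 | 50% | 12.7% | 11.7% | 10.3% | 8.8% |
| EPT and VAS ≤ 3 | 70% | 12.1% | 11.4% | 11.0% | 9.9% |
| EPT and VAS ≤ 3 | 90% | 12.8% | 12.9% | 11.7% | 10.1% |

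A separate simulation (5,000 trials per scenario, success 50-90%, correlation up to 0.9) gave 8.3-12.5%. Together these give about 8-13%.

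**Step 4: where the excess comes from.** With EPT-only success, chi-square or log-rank alone gives 5.9-7.6%, against 9.75% if the two were independent. Most of the excess therefore comes from adding VAS.

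**Step 5: direction.** With no true difference the errors fall about equally either way. Half of 8-13% is about 4-6.5% for a false result favouring buffering, against 2.5% for a single two-sided 5% test.

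**Step 6: the remedies.** In a fixed sequence, a false claim when nothing differs requires the first test to be falsely significant. The exact size of the uncorrected chi-square at 20 per group is 3.9-5.3% for success rates of 50-90%, and its power stays at 81%. Splitting the level equally (0.05/3 = 0.0167, z = 2.394) gives (1.789 − 2.394 × 0.648) / 0.583 = 0.407, or 66% power; 27 per group would then be needed for 80%.

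**The case against.** The strongest reply is that the chi-square comparison is already the implied primary, since the sample size rests on it alone. The documents never promise a 5% rate across all tests. If only the chi-square result carries the conclusion, its error rate is about 5%. This stands in part: the 5% is a per-test level, and the inflation is conditional on any one result being claimable. But the priority has to be inferred, and nothing in the plan rules out a claim resting on onset or VAS.

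Four stronger readings are tempting and should not be drawn:

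- *That the error is at least 10%.* This holds for weak to moderate correlation, but the table falls to 8.7% at a correlation of 0.9 and 50% success. A continuity-corrected chi-square would lower the range further, to 7.3-11.0% in one simulation.
- *That this is the chance of falsely concluding that buffering works.* The figure counts two-sided errors in both directions.
- *That two tests on one event make matters worse.* Overlap lowers the total relative to independent tests. If VAS enters the success definition, the chi-square and log-rank tests no longer use the same event.
- *That the plan breaks its own familywise guarantee.* It gives none.

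It can also be said that a fixed sequence is one choice among several. That is fair: labelling one primary would settle the main point. The sequence has the advantage of leaving the sized test's power intact while stating how the other two may be used.

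**Conclusion.** The concern holds in a conditional form. With three tests at two-sided 5%, no named primary and no order, a reader who may claim a difference from any one of them faces about an 8-13% chance of a false claim when the formulations do not differ. That is roughly double the nominal level, and about half of those errors would favour buffering.

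The size rests on assumed null success rates, an assumed VAS-onset correlation and an uncorrected chi-square. It changes little between the two success definitions simulated. Three tests is the smallest count the text supports: chi-square and log-rank tests are written in the plural and soft-tissue onset time is also recorded, so further comparisons would raise the figure.

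The sample size and stated power are sound for the chi-square test. What is missing is the statement that this test decides the trial.

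**What to change.** In the Statistical Analysis section:

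1. Name as primary the chi-square test of the proportion with profound pulpal anesthesia, at two-sided 5%.
2. State one success definition for that test. Anesthetic Testing and Documentation currently supports both EPT = 80 and VAS of 3 or lower, and a primary test with two available definitions does not secure 5%. The investigators must choose; this point does not depend on which.
3. Label the log-rank and VAS tests, and any further test such as soft-tissue onset time, as secondary. Test log-rank at 5% only if the primary is significant, and VAS at 5% only if log-rank is significant.
4. After the first non-significant step, report the remaining comparisons as estimates with 95% confidence intervals and make no efficacy claim from them.

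No participants are added and chi-square power at 20 per group is unchanged at 81%. The price is that a positive onset or VAS result after a negative primary is exploratory only.

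The section is written in the past tense. If the data have already been analysed, the order can govern only how results are labelled and interpreted, and it must not be presented as prespecified.

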mandible. Soft tissue anesthesia was considered profound when the patient subjectively attested that their lip, chin, and tongue on the respective treatment side felt “full” or “numb,” and a light stimulation with the tip of an explorer did not elicit any sensation other than pressure as compared to a “sharp” feeling the contralateral side. In the event that the patient denied any signs of soft tissue anesthesia (absolutely no change in feeling) 10 minutes after the 2 cartridges of anesthetic were given via inferior alveolar nerve block (IANB), then the blocks were to be considered “missed,” and the patient would need to be re-blocked as clinically appropriate. This situation would be grounds for withdrawing the patient from the study (with documentation) since a lack of anesthesia following the protocol cannot be attributed to the anesthetic formulation itself but rather operator technique/variable patient anatomy.

Once the patient attested to having soft tissue anesthesia, the amount of time surpassed since being blocked was documented on the designated datasheet, and the supplemental buccal and lingual infiltrations were then administered as previously described. The student researcher or other residents waited 2 minutes after all 3 cartridges of local anesthesia had been administered and then obtained an updated EPT reading on the tooth being treated. An EPT=80 (maximum stimulation) indicated profound pulpal anesthesia, and the endodontic access was initiated. An EPT \neq 80 indicated a need to wait an additional time. We retested the tooth being treated using EPT at 2-minute intervals until EPT=80 or when a maximum of 20 minutes had passed since administering 2 IANBs. According to Whitcomb et al., waiting 10-15 minutes after administering the IANB should be adequate time to allow the onset of pulpal anesthesia in molars. Once EPT=80, the reading was reconfirmed in order to get a consecutive EPT=80 a minute after the initial reading. Participants who did not demonstrate *total* soft tissue and/or pulpal anesthesia within 20 minutes would be categorized as a failure and further managed

according to the best clinical practice (additional block/supplementary injections) so that the endodontic treatment could continue appropriately. After confirming soft tissue anesthesia and 2 consecutive EPT=80, the endodontic treatment could begin.

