Upon the completion of the pulpotomy, the patient was shown the same Visual Analog Scale to re-assess their level of comfort. However, any discomfort recognized during the pulpal access or pulpotomy paused the procedure, and the VAS was shown immediately. Patients who indicated moderate or severe pain (VAS scores of 4 or higher) elicited from the tooth undergoing treatment upon pulpal access or a complete pulpotomy were categorized as an anesthesia failure (lack of profoundness) and appropriately managed as previously described. Patients who indicated no pain or mild pain (VAS scores of 3 or lower) were categorized as an anesthesia success (obtained profoundness), and the endodontic treatment continued. When co-residents rendered the clinical endodontic treatment, they recorded and reported these failures to the student researcher after appropriately treating their patient. The student researcher charted the data for each uniquely identified study participant regarding the initial EPT readings (treated tooth and control), the amount of time taken to reach both soft tissue and pulpal anesthesia, VAS scores after both cold testing (baseline) and pulpotomy, and any other conditions that may have led to a “failed” profoundness of anesthesia.

STUDY PROCEDURES

1. Reviewed medical history as a standard of care for endodontic treatment (about 3-5 minutes)
2. Standard of care dental exam with sensibility testing that established baseline EPT reading and VAS score (about 5-10 minutes)

3. Reviewed inclusion/exclusion criteria using data collected in steps 1 and 2 for a standard of care to ensure that the subject qualified to continue with the study (about 3 minutes)
4. Performed consenting procedures for both the Non-surgical Root Canal Therapy (NSRCT) and the research study (about 5-10 minutes)
5. A trained research assistant prepared the cartridges of the type of anesthetic formulation (buffered vs. unbuffered) determined by the randomization scheme in a separate room immediately prior to it being administered. The assistant made a record using a unique identifying code for the type given to each patient. The Onpharma Onset protocol was used when indicated. The assistant “prepared” the unbuffered cartridges in the same amount of time as required for the buffered cartridges, as well as “puncturing” the unbuffered cartridges with the Onset pen so that each cartridge had a uniform appearance (about 3 minutes)

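### The planned VAS comparison can include scores taken after additional anesthetic, and neither using those scores nor dropping EPT failures gives a clean pain comparison in all patients

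*Combined protocol and SAP*

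**What the plan says.** All references are to the combined protocol and SAP.

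- **Analysis.** Statistical Analysis says: "Comparisons of the VAS results were made using a" "Wilcoxon Rank Sum test". It attaches no analysis set, rule for rescued patients or role for the baseline score. The sample-size text says "Up to 60 subjects were randomized to ensure that 40 evaluable subjects could complete the study", and evaluable is not defined.
- **Which score.** Step 10 of Study Procedures says the VAS after chamber access/pulpotomy is recorded and analysed. The list of charted data in Anesthetic Testing and Documentation has two VAS entries, one after cold testing (baseline) and one after pulpotomy.
- **EPT gate.** "After confirming soft tissue anesthesia and 2 consecutive EPT=80, the endodontic treatment could begin". If this is not reached by 20 minutes, step 9b says "anesthesia was considered a failure, and additional local anesthetic was administered as clinically appropriate", and the testing section makes clear that treatment then goes on.
- **Pain during access.** "any discomfort recognized during the pulpal access or pulpotomy paused the procedure, and the VAS was shown immediately". A patient scoring 4 or higher is "categorized as an anesthesia failure (lack of profoundness) and appropriately managed as previously described". The earlier description referred to is additional block or supplementary injections.
- **Powered comparison.** With 20 per group, "the study had an 80% power to detect a difference between 90% and 50% of subjects who achieved profound pulpal anesthesia".

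**The concern.** Two groups receive more anesthetic before the pulpotomy is finished: 20-minute EPT failures, and patients who pause with a VAS of 4 or higher. An EPT failure has no procedural VAS from before rescue; whatever exists is post-rescue. A paused patient can have a pause score taken before rescue and a completion score taken after it. The documents point to the score after access/pulpotomy without saying which of the two is meant, so an analyst who follows the plan can put post-rescue scores into the Wilcoxon test.

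At the plan's 90% v 50%, the expected failures are 20 × 0.10 = 2 and 20 × 0.50 = 10. This count holds whether success means EPT=80 alone or EPT=80 plus a VAS of 3 or lower, and both kinds of failure lead to more anesthetic. With up to half of one arm affected, the way these patients are scored can change the trial's conclusion about pain.

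**Working it through.** **The plan's own figure.** Chi-square power, 20 per arm, 0.9 v 0.5, two-sided 5%; pooled proportion 0.7:

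power = Φ[(0.4 − 1.96·√(2·0.7·0.3/20)) / √((0.9·0.1 + 0.5·0.5)/20)] = Φ[(0.4 − 0.284)/0.130] ≈ 81.3%.

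The stated 80% is reproduced. No power is stated for VAS.

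**Inputs.** From the documents: 20 per arm, 5% two-sided, a 0-10 scale, the cut at 4, the EPT gate, and 90% v 50%. Assumed, because the documents give no values: VAS mean 2.5 and SD 2.2; correlation r between EPT failure and pain of 0, 0.3 or 0.5; rescue lowering pain by 0, 0.5 or 1 SD (1 SD = 2.2 points).

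**Model.** EPT sensitivity and pain are bivariate normal with correlation r. EPT failure is the upper tail at each arm's rate. VAS = round(2.5 + 2.2 × pain − benefit), limited to 0-10. A post-rescue score subtracts the rescue effect. The test is a tie-corrected Wilcoxon, with 10,000 runs per scenario.

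**Case 1: EPT success 90/50, no pain effect.** Rejection in the wrong direction (against the arm with fewer EPT failures; nominal 2.5%):

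| Handling of EPT failures | Wrong-direction rejection |
|---|---|
| Dropped, r = 0 / 0.3 / 0.5 | 2.5 / 5.7 / 10-11% |
| Post-rescue score, no rescue effect | 2-3% |
| Post-rescue score, 0.5 SD | 8-9% |
| Post-rescue score, 1 SD | 18-24% |

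Dropping makes the better arm look 0.00 / 0.35 / 0.57 points worse. For r 0.3-0.5, VAS mean 1.5-3.5 and SD 1.6-2.8, the ranges are 5-11% (dropped), 7-9% (0.5 SD) and 18-25% (1 SD).

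**Case 2: EPT success 95/75 with a 2.5-point benefit.** Success on EPT and VAS together is then 90/51, 90/54 and 91/57 at the three values of r. The benefit appears as about −1.77 on the scale because scores cannot go below 0.

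| Scores used | Power, r = 0 / 0.3 / 0.5 |
|---|---|
| All patients, unrescued (benchmark) | 89-90% |
| EPT=80 patients only | 83 / 77 / 74% |
| EPT failures post-rescue, 1 SD | 71 / 75 / 78% |
| Every rescued patient's final score, 1 SD | 67 / 72 / 76% |

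In the last row the difference shrinks from −1.77 to −0.98 / −1.00 / −1.04, a loss of (1.77 − 1.04)/1.77 = 41% to (1.77 − 0.98)/1.77 = 45%. No sign change occurs. If r = 0.5 and the inputs are reset so that joint success is 90/50 (EPT 95/63, benefit 2.34), power is 86% on unrescued pain, 54% in EPT=80 patients and 57% with EPT failures scored post-rescue.

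**Case 3: EPT success 70/70.** With no pain effect there is no bias (rejection 4-5%). With a 1.5-point benefit, among EPT=80 patients, using the final rather than the pre-rescue score (1 SD) shrinks −1.17 / −1.11 / −1.08 to −0.74 / −0.72 / −0.72, and power falls from 36-39% to 30-34%. This isolates the effect of the paused patients alone.

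**Baseline adjustment.** EPT=80 set, 95/75, 2.5 points, r = 0.3; ρ is the correlation of baseline with procedural VAS. Power, Wilcoxon to rank ANCOVA: 76.8 to 76.4% (ρ = 0), 77.8 to 78.6% (0.2), 76.9 to 80.5% (0.3), 76.5 to 84.5% (0.5).

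**The case against.** - **A score is named.** This stands: step 10 and the charted list point to the access/pulpotomy VAS. A reader might infer that the plan names no score at all, which goes too far. What remains open is pause v completion score and raw score v change from baseline.
- **The pause score may replace the completion score.** The wording allows this, and that score precedes rescue. Nothing says that a failed patient is re-scored after rescue and that score analysed. So a reader may not infer that post-rescue scores were used, only that the plan permits it. For EPT failures this reading does not help, because they have no pre-rescue procedural score.
- **The wrong-direction result needs an extreme null.** This also stands. With a 1-point benefit at 90/50 and r = 0.3, wrong-direction rejection is only about 0.5% (dropped) and 1.6% (post-rescue, 1 SD), below the nominal 2.5%. The usual consequence is a diluted benefit.
- **Restricting to EPT=80 patients is itself dropping.** Correct. It breaks the randomized comparison and can have less power than post-rescue scoring: 77% v 83% at 95/75, r = 0.3 and a 0.5-SD rescue effect. It cannot serve as the single clean answer.
- **Rank ANCOVA is a preference.** In part. The gain is nil at ρ = 0 and the documents give no ρ. But baseline VAS is already collected, so adjustment costs little, provided the stated Wilcoxon is shown beside it.

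**Conclusion.** The concern holds in a limited form. The plan permits post-rescue scores in the VAS comparison. If rescue lowers pain, they shrink a real difference; if EPT success also differs by arm, they count against the better formulation. Dropping EPT failures biases the test when EPT failure is linked to pain. Without that link it only loses patients.

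The size rests on the assumed VAS mean, SD, correlation and rescue effect. With a 1-SD rescue effect and final scores throughout, about −1.77 becomes about −1.0. A reader might infer that the better formulation will look worse. The documents do not support that: it needs a near-zero pain effect together with unequal EPT success. Nor does the point undermine the trial's main result. VAS is not the powered comparison, and the chi-square test and sample size are unaffected. Only the pain conclusion is limited. The change should be made, but it is not critical to the trial.

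**What to change.** Put the following in Statistical Analysis:

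1. Where a patient has a score from before additional anesthetic, analyse the highest such VAS at access or pulpotomy, not a later post-rescue score.
2. Compare arms by rank ANCOVA on the baseline cold-test VAS, with the unadjusted Wilcoxon result beside it.
3. Because EPT failures have no pre-rescue procedural score, show the VAS result two ways. (a) Among patients with EPT=80, labelled as conditional on EPT success and not as the effect in all patients. (b) With 20-minute failures ranked worst, labelled as a composite of anesthesia failure and pain. State that neither is a clean randomized comparison of pain.
4. Report EPT failures, patients given additional anesthetic and missed-block withdrawals by arm.

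Label any change made after unblinding as post hoc; the document is written mostly in the past tense, so this may apply.

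**Cost.** Text and a few lines of code. Baseline VAS, EPT outcome and access discomfort are already recorded. Someone must check that the datasheet shows whether each score came before or after additional anesthetic. The pain conclusion becomes narrower. Analysis (a) keeps its selection (10-11% wrong-direction rejection in case 1 at r = 0.5). Analysis (b) rejects in 43-62% of case 1 trials with no pain effect at all, and at 70/70 with a 1.5-point benefit it has 15-16% power against 36-39% for (a), hence the labels. Nothing here changes clinical management.

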applicable, this diagnosis was specifically confirmed on the same day that the warranted endodontic treatment was rendered. Prospective study participants were given brief instructions on cold and EPT usage/expectations. Regarding the cold testing, a cotton pellet was held with cotton forceps and thoroughly sprayed with Endo-Ice (Coltene) at -26.2 Celsius until the cotton pellet was soaked. The cotton pellet was then applied to the mid-buccal, natural surface of the tooth, and the patient's response was monitored. The soaked cotton pellet was removed once the patient felt a painful sensation on the tested tooth or if no sensation was felt after 10 seconds of an application. If pain was felt, the amount of time until the sensation subsided was measured. A continued pain for 10 seconds or longer was considered "lingering" pain. Exaggerated or lingering pain, as compared to adjacent or control teeth, was considered acute pain and further quantified on the Wong-Baker FACES Visual Analog Scale (VAS), ranging from 0-10. Patients were immediately presented with this VAS, and their baseline response was recorded. After any previously induced pain had subsided, an electrical pulp testing exam was done using an Electric Pulp Tester (EPT) Sybron Analytic to establish a baseline reading. A 2-3 mm dab of toothpaste was placed on the dried buccal tooth structure. The tip of the EPT was placed on the toothpaste and the EPT was activated once the patient held the end of the wand, thereby completing the circuit. The test was stopped when the patient felt pain or a "tingling" sensation after letting go of the wand or if the measurements reached a maximum value of 80. The EPT number was recorded by the resident on a designated data sheet. Ultimately, a diagnosis of symptomatic irreversible pulpitis was made if the patient had acute, lingering pain cold as compared to the control tooth.

BUFFERED ANESTHETIC PREPARATION

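### Baseline pain and EPT are recorded, but no baseline-adjusted analysis is specified and the VAS score that the Wilcoxon test compares is not named

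*Combined protocol and SAP*

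**What the plan says.** The Diagnosis section has each participant rate the cold-test response on the 0-10 scale: "Patients were immediately presented with this VAS, and their baseline response was recorded". A baseline EPT reading follows. Under Anesthetic Testing and Documentation, the charted items include the initial EPT of the treated and control teeth and "VAS scores after both cold testing (baseline) and pulpotomy". The second rating uses the same scale as the first.

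The Statistical Analysis section gives three between-arm analyses: a chi-square test for the proportion with profound pulpal anesthesia, Kaplan-Meier curves with a log-rank test for time to it, and, for pain, "Comparisons of the VAS results were made using a" "Wilcoxon Rank Sum test". It names no covariate, stratification factor, change score or adjusted model. On error rate it says "A 5% significance level was used for all tests".

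The sample size rests on the success proportion alone. The power statement is "With a sample size of 20 subjects per group, the study had an 80% power", and the target attached to it is "to detect a difference between 90% and 50% of subjects who achieved profound pulpal anesthesia". The Recruitment and Enrollment section describes randomization by order of entry and names no baseline stratification.

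**The concern.** There are two gaps.

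- **Specification.** Two VAS scores exist per participant. The Wilcoxon sentence could refer to the baseline score, the pulpotomy score, both, or the change. These are different analyses, and the choice should not be open once the data are seen.
- **Unused baseline information.** Cold-test VAS is a pre-treatment reading on the scale later used for the pain outcome. If the two scores are correlated, an unadjusted comparison leaves explainable variance in the outcome and carries any chance baseline difference into the observed effect. With 20 per arm such differences can be appreciable, and neither the randomization as described nor the analysis addresses them.

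At stake are the precision of the VAS comparison and how one small trial's VAS result is read if the arms happen to differ at baseline.

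**Working it through.** **Inputs.** From Statistical Analysis: 20 per arm, 90% versus 50% success, 80% power, and "Calculations were based on a chi-square test with a two-sided 5% significance level". Assumed, because the documents do not give them: the correlation r between baseline cold-test VAS and pulpotomy VAS (0 to 0.5), and the size of the VAS effect.

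**1. The plan's own figure.** Chi-square, pooled variance under the null, no continuity correction:

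power = Φ[(0.4 − 1.96·√(2·0.7·0.3/20)) / √((0.09 + 0.25)/20)] = Φ[(0.4 − 0.284)/0.130] = 0.813.

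The stated 80% reproduces.

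**2. Chance imbalance.** The between-arm difference in mean baseline has standard error √(2/20) = 0.316 SD, so its 95% range is ±0.62 SD.

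- P(difference above 0.3 SD) = 2[1 − Φ(0.3/0.316)] = 34%.
- P(difference above 0.5 SD) = 2[1 − Φ(0.5/0.316)] = 11%.

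**3. What an imbalance does.** A 0.5 SD baseline difference moves the unadjusted outcome difference by 0.5r SD, or 0.5r/0.316 standard errors: 0.16 SE at r = 0.1, 0.47 at r = 0.3, 0.79 at r = 0.5. Given that imbalance, the unadjusted statistic under no effect has mean 0.5r/0.316 and variance 1 − r². The conditional two-sided false-positive rate is then about 6.5% at r = 0.3 and 9% at r = 0.5. Averaged over all randomizations it stays at 5%.

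**4. Power on a continuous-type outcome.** Take a difference with 80% unadjusted power: (1.96 + 0.84)·0.316 = 0.886 SD. Adjusting for one covariate multiplies the variance by (1 − r²)(1 + 1/36), where the second factor is the cost of estimating the slope with 40 participants.

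| r | Variance factor | Adjusted power | Change (points) |
|---|---|---|---|
| 0 | 1.028 | 78.9% | −1.1 |
| 0.3 | 0.935 | 82.6% | +2.6 |
| 0.5 | 0.771 | 89.1% | +9.1 |

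Break-even is at r² = 1/37, so r is about 0.16.

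**5. Wilcoxon versus rank ANCOVA, simulated on a rounded 0-10 scale, 20 per arm.** Two effect sizes were used. The first, 0.9 SD, is an assumption. The second, 1.28 SD, is the latent-normal shift implied by the plan's 90% versus 50% if success is read as VAS of 3 or lower: Φ⁻¹(0.9) − Φ⁻¹(0.5) = 1.28. It also assumes an outcome SD of 3 and baseline scores from 4 to 10.

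| r | 0.9 SD: Wilcoxon / adjusted | 1.28 SD: Wilcoxon / adjusted |
|---|---|---|
| 0 | 72% / 71% | 95.4% / 95.2% |
| 0.3 | 71% / 74% | 95.0% / 95.9% |
| 0.5 | 72% / 80% | 95.3% / 97.8% |

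**6. The success proportion.** Simulated at 90% versus 50%, with adjustment by a linear model, power unadjusted and adjusted is 84.5% and 83.4% at r = 0, 83.9% and 84.2% at r = 0.3, and 82.9% and 86.4% at r = 0.5. The type I error of the unadjusted chi-square test was 4.4% to 5.1%.

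**The case against.** The strongest case against runs as follows.

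- **Validity.** Chance imbalance is already allowed for in the error rate of an unadjusted test under randomization. This stands: no planned test is invalid.
- **Correlation.** Nothing in the documents supports a substantial r. Baseline VAS is a response to cold on an unanesthetized tooth, whereas the outcome is pain at access or pulpotomy under anesthesia. Entry requires an exaggerated, lingering cold response, which may narrow the baseline range. This stands, and below r of about 0.16 adjustment costs a little precision.
- **Effect size.** At the effect implied by the trial's own success rates, the Wilcoxon test already has about 95% power and adjustment adds roughly 1 to 2.5 points. This stands as the lower end of the range.
- **The VAS wording.** A reader might infer that no between-arm test uses baseline VAS at all. The documents do not support that, because the wording could cover the baseline score or the change. Step 10 of Study Procedures points to the score after access or pulpotomy, but it does not define the test. For baseline EPT the absence is clear: it enters no listed test.

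What remains is that no reading of the Wilcoxon sentence supplies a covariate-adjusted comparison, and that the sentence needs a definition whatever r is. The trade-off is also uneven: about 1 power point lost if baseline is uninformative, against up to about 9 gained at r = 0.5.

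**Conclusion.** The point holds as a matter of specification and possible efficiency in the VAS analysis. The score under test is undefined and no baseline-adjusted analysis is prespecified, although the baseline data are collected. The probability of a baseline difference above 0.5 SD is about 11%. Adjusting the VAS comparison changes power by about −1 point at r = 0, +1 to +3 at r = 0.3, and +2.5 to +9 at r = 0.5. These figures rest on an assumed r and an assumed effect.

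Two stronger readings should be resisted. A reader might infer that the trial definitely gives away precision, equivalent to about a third more participants. That figure is 1/(1 − 0.5²) = 1.33; it needs r = 0.5, which the documents do not support. A reader might also infer that the trial's results or stated power are compromised. They are not: the 80% reproduces at 81.3% on an unadjusted test, and that endpoint would gain about 0 points at r = 0.3 and 3.5 at r = 0.5. No magnitude can be given for adjusting time to anesthesia for baseline EPT, because the documents do not show that baseline EPT predicts onset.

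**What to change.** In Statistical Analysis:

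1. State that the VAS comparison is of the pulpotomy score.
2. Prespecify a baseline-adjusted comparison of that score, by rank ANCOVA or a proportional-odds model with arm and baseline cold-test VAS. Report the effect with its 95% CI alongside the Wilcoxon test.
3. Name in advance which of the two is the main VAS test.
4. Optionally, add a Cox model with arm and the treated tooth's baseline EPT as a supportive analysis beside the log-rank test.

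The chi-square test and the sample size need no change. The cost is a short addition to the text and one extra model, with no new measurements or participants. The downside is a loss of about 1 power point on the VAS comparison if the adjusted test is made the main one and baseline proves unrelated to outcome.
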